5.3 Definitions of Evaluability

In order to be evaluable for the primary objective (ctDNA negativity at C3D1), a patient must have blood drawn to assess ctDNA at that time point. Patients in Stage 1 who discontinue treatment prior to C3D1 will be replaced; patients in Stage 2 who discontinue treatment prior to C3D1 will not be replaced.

All patients who receive any study treatment are evaluable for toxicity. Patients are evaluated from first receiving study treatment until a 90-day follow up after the conclusion of treatment or death.

All patients are evaluable for disease response unless they discontinue participation prior to having any disease assessment.

5.4 Concomitant Therapy and Supportive Care Guidelines

If a patient experiences an infusion-related reaction with any previous infusion of atezolizumab or tiragolumab, premedication with an antihistamine and/or antipyretic medication may be administered for subsequent doses at the discretion of the investigator.

5.4.1 Permitted Therapy

Patients are permitted to use the following therapies during the study:

- Oral contraceptives with a failure rate of < 1% per year
- Hormone-replacement therapy
- Prophylactic or therapeutic anticoagulation therapy (such as warfarin at a stable dose or low-molecular-weight heparin)
- Inactivated influenza vaccinations
- Megestrol acetate administered as an appetite stimulant
- Mineralocorticoids (e.g., fludrocortisone)
- Corticosteroids administered for COPD or asthma
- Low-dose corticosteroids administered for orthostatic hypotension or adrenocortical insufficiency

Premedication with antihistamines, antipyretics, and/or analgesics may be administered for the second and subsequent infusions only, at the discretion of the investigator.

In general, investigators should manage a patient's care (including preexisting conditions) with supportive therapies other than those defined as cautionary or prohibited therapies as clinically indicated, per local standard practice. Patients who experience infusion-associated symptoms may be treated symptomatically with acetaminophen, ibuprofen, diphenhydramine, and/or H₂-receptor antagonists (e.g., famotidine, cimetidine), or equivalent medications per local standard practice. Serious infusion-associated events manifested by dyspnea, hypotension, wheezing, bronchospasm, tachycardia, reduced oxygen saturation, or respiratory distress should be managed with supportive therapies as clinically indicated (e.g., supplemental oxygen and β ₂-adrenergic agonists).

5.4.2 Cautionary Therapy for Atezolizumab- and Tiragolumab-Treated Patients

5.4.2.1 Corticosteroids, Immunosuppressive Medications, and TNF- α Inhibitors

Systemic corticosteroids, immunosuppressive medications, and TNF- α inhibitors may attenuate potential beneficial immunologic effects of treatment with atezolizumab. Therefore, in situations in which systemic corticosteroids, immunosuppressive medications, or TNF- α inhibitors would be routinely administered, alternatives, including antihistamines, should be considered. If the alternatives are not feasible, systemic corticosteroids, immunosuppressive medications, and TNF- α inhibitors may be administered at the discretion of the investigator.

Systemic corticosteroids or immunosuppressive medications are recommended, at the discretion of the investigator, for the treatment of specific adverse events when associated with atezolizumab and/or tiragolumab therapy.

5.4.2.2 Herbal Therapies

Concomitant use of herbal therapies is not recommended because their pharmacokinetics, safety profiles, and potential drug-drug interactions are generally unknown. However, herbal therapies not intended for the treatment of cancer may be used during the study at the discretion of the investigator.

5.4.3 Prohibited Therapy

Use of the following concomitant therapies is prohibited as described below:

- Concomitant therapy intended for the treatment of cancer (including, but not limited to, chemotherapy, hormonal therapy, immunotherapy, radiotherapy, and herbal therapy), whether health authority-approved or experimental, is prohibited for various time periods prior to starting study treatment, depending on the agent, and during study treatment, until disease progression is documented and the patient has discontinued study treatment.
- Investigational therapy within 42 days prior to initiation of study treatment and during study treatment. Of note, COVID vaccines are not considered an investigational therapy.
- Live, attenuated vaccines (e.g., FluMist®) are prohibited within 4 weeks prior to initiation of study treatment, during study treatment, for 90 days after the final dose of tiragolumab, and for 5 months after the final dose of atezolizumab.
- Systemic immunostimulatory agents (including, but not limited to, interferons and IL 2) are prohibited within 4 weeks or 5 drug-elimination half-lives (whichever is longer) prior to initiation of study treatment and during study treatment because these agents could potentially increase the risk for autoimmune conditions when given in combination with atezolizumab and tiragolumab.

5.5 Women of Childbearing Potential

Women must remain abstinent or use contraceptive methods with a failure rate of < 1% per year during the treatment period and for 90 days after the final dose of tiragolumab and 5 months after the final dose of atezolizumab.

A woman is considered to be of childbearing potential if she is postmenarchal, has not reached a postmenopausal state (≥ 12 continuous months of amenorrhea with no identified cause other than menopause), and is not permanently infertile due to surgery (i.e., removal of ovaries, fallopian tubes, and/or uterus) or another cause as determined by the investigator

(e.g., Müllerian agenesis). The definition of childbearing potential may be adapted for alignment with local guidelines or regulations.

Examples of contraceptive methods with a failure rate of < 1% per year include bilateral tubal ligation, male sterilization, hormonal contraceptives that inhibit ovulation, hormone-releasing intrauterine devices, and copper intrauterine devices.

The reliability of sexual abstinence should be evaluated in relation to the duration of the clinical trial and the preferred and usual lifestyle of the patient. Periodic abstinence (e.g., calendar, ovulation, symptothermal, or postovulation methods) and withdrawal are not adequate methods of contraception.

With a female partner of childbearing potential, men who are not surgically sterile must remain abstinent or use a condom plus an additional contraceptive method that together result in a failure rate of < 1% per year during the treatment period, for 90 days after the final dose of tiragolumab. Men must refrain from donating sperm during this same period.

With a pregnant female partner, men must remain abstinent or use a condom during the treatment period for 90 days after the final dose of tiragolumab to avoid exposing the embryo.

The reliability of sexual abstinence should be evaluated in relation to the duration of the clinical trial and the preferred and usual lifestyle of the patient. Periodic abstinence (e.g., calendar, ovulation, symptothermal, or postovulation methods) and withdrawal are not adequate methods of contraception.

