3.2 Step Two (Randomization and Treatment) Eligibility

3.2.1 Inclusion Criteria

1. Positive ctDNA test.
2. Normal bone marrow and organ function as defined below:
 - a. Absolute neutrophil count $\geq 1,500/\text{mcL}$
 - b. Lymphocyte count $\geq 500/\text{mcL}$
 - c. Platelets $\geq 100,000/\text{mcL}$
 - d. Hemoglobin ≥ 9.0 g/dL (patients may be transfused to meet this criterion)
 - e. Total bilirubin ≤ 1.5 x IULN or direct bilirubin \leq IULN for participants with total bilirubin levels > 1.5 x IULN; patients with known Gilbert disease must have total bilirubin ≤ 3 x IULN
 - f. AST(SGOT)/ALT(SGPT) ≤ 2.5 x IULN
 - g. Alkaline phosphatase ≤ 2.5 x IULN
 - h. Creatinine clearance ≥ 45 mL/min by Cockcroft-Gault
 - i. Serum albumin ≥ 2.5 g/dL
 - j. INR or PT ≤ 1.5 x IULN unless participant is receiving anticoagulant therapy as long as PT or aPTT is within therapeutic range of intended use of anticoagulants
 - k. aPTT ≤ 1.5 x IULN unless participant is receiving anticoagulant therapy as long as PT or aPTT is within therapeutic range of intended use of anticoagulants
3. ECOG performance status ≤ 1 (see Appendix A)

4. The effects of atezolizumab and tiragolumab on the developing human fetus are unknown. For this reason, women of childbearing potential and men must agree to use adequate contraception (hormonal or barrier method of birth control, abstinence) prior to study entry and for the duration of study participation, for 90 days after the final dose of tiragolumab, and for 5 months after the final dose of atezolizumab. Should a woman become pregnant or suspect she is pregnant while participating in this study, she must inform her treating physician immediately. Men treated or enrolled on this protocol must also agree to use adequate contraception prior to the study, for the duration of the study, and 90 days after completion of the study

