6.2 Treatment Interruptions

Study treatment may be temporarily suspended as appropriate for management of toxicity. On the basis of the available characterization of mechanism of action, tiragolumab may cause adverse events similar to but independent of atezolizumab, may exacerbate the frequency or severity of atezolizumab related adverse events, or may have non overlapping toxicities with atezolizumab. Because these scenarios may not be distinguished from one another in the clinical setting, immune mediated adverse events should generally be attributed to both study drugs, and dose interruptions or treatment discontinuation in response to immune mediated adverse events should be applied to both atezolizumab and tiragolumab.

In the adjuvant setting, atezolizumab and tiragolumab may be held for a maximum of 12 weeks. If tiragolumab is interrupted for > 12 weeks for any reason, the patient must permanently discontinue tiragolumab treatment, but may continue atezolizumab if there is no contraindication and after discussion with the PI to determine whether the toxicity is considered related to tiragolumab and/or to the combination. An exception can be made if in the judgment of the investigator, the patient is likely to derive clinical benefit from resuming tiragolumab after a hold of > 12 weeks. In this case, tiragolumab may be restarted with the approval of the PI. If atezolizumab is interrupted for > 12 weeks, the patient must permanently discontinue atezolizumab. However, if, in the judgment of the investigator, the patient is likely to derive clinical benefit from atezolizumab after a hold of > 12 weeks, atezolizumab may be restarted with the approval of the PI. Continued dosing of patients with single agent atezolizumab will require that all other study eligibility criteria continue to be met. Continued administration of single agent tiragolumab after permanent discontinuation of atezolizumab is not permitted.

If a patient must be tapered off steroids used to treat adverse events, atezolizumab and/or tiragolumab may be withheld for additional time beyond > 12 weeks from the last dose until steroids are discontinued, or until steroids are reduced to prednisone dose (or dose equivalent) ≤ 10 mg/day. The acceptable length of interruption will depend on an agreement with the PI.

Dose interruptions for reason(s) other than toxicity may be allowed with PI approval.

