14.6 Study Population

If the study stops after stage 1, we will screen 144 melanoma patients who had undergone complete resection. Among them, 18 ctDNA-positive patients being treated with the combination of atezolizumab and tiragolumab will be compared to a historical control and 18 ctDNA-positive patients on atezolizumab monotherapy will be analyzed as a descriptive comparison.

If we continue the study after stage 1, the study will screen 244 patients in total. Among them, 43 ctDNA-positive patients being treated with the combination of atezolizumab and

tiragolumab will be compared to a historical control and 18 ctDNA-positive patients on atezolizumab monotherapy will be analyzed as a descriptive comparison.

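### Sections 3.2.1 and 5.5 give men different post-treatment contraception periods, and 5.5 states none for men on atezolizumab alone

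*Combined protocol and SAP*

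**What the plan says.** Section 3.2.1 item 4 contains two statements that bind men.

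- Its first rule covers both sexes: "women of childbearing potential and men must agree to use adequate contraception". The post-treatment part reads "for 90 days after the final dose of tiragolumab, and for 5 months after the final dose of atezolizumab".
- Its last sentence is for men only and is tied to neither drug: "for the duration of the study, and 90 days after completion of the study".

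Section 5.5 states the rule again, separately by sex.

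- Women: "during the treatment period and for 90 days after the final dose of tiragolumab and 5 months after the final dose of atezolizumab". Both drugs are named.
- Men who are not surgically sterile and have a partner of childbearing potential: "during the treatment period, for 90 days after the final dose of tiragolumab. Men must refrain from donating sperm during this same period". Only tiragolumab is named.
- Men with a pregnant partner: "men must remain abstinent or use a condom during the treatment period for 90 days after the final dose of tiragolumab". Again only tiragolumab is named.

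Two other parts of the protocol decide whom this affects. Stage 1 has an arm that never receives tiragolumab; Section 14.6 says that "18 ctDNA-positive patients on atezolizumab monotherapy will be analyzed as a descriptive comparison". Section 6.2 also provides that a patient whose tiragolumab has been interrupted for more than 12 weeks, and so must stop it permanently, "may continue atezolizumab if there is no contraindication and after discussion with the PI".

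**The concern.** A rule that protects patients' partners should give one answer for one man. Here a site that counsels from the eligibility item and a site that counsels from Section 5.5 would give the same man different end dates for contraception. A site using 5.5 alone would find no post-treatment end date for a man in the atezolizumab arm, because he has no last tiragolumab dose to count from. The sperm donation restriction appears only in 5.5 and takes its length from the same sentence, so it has the same gap. What is at stake is consistent counselling and a clear standard for compliance. The statistical analysis does not depend on it.

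**Working it through.** There is no statistical figure to reproduce. The check sets the stated periods side by side for each way in which a man can be treated. I take 5 months as 150 to 153 days, which is an assumption, and count from the last dose.

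| Situation | 3.2.1 item 4, first rule | 3.2.1 item 4, last sentence | Section 5.5 |
|---|---|---|---|
| Both drugs end on the same day | 5 months (150 to 153 days) | 90 days after study completion | 90 days |
| Atezolizumab alone | 5 months after last atezolizumab | 90 days after study completion | Treatment period only |
| Tiragolumab stopped, atezolizumab continued | 5 months after last atezolizumab | 90 days after study completion | Treatment period, plus whatever is left of the 90 days |

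**Both drugs ending together.** The difference between the first eligibility rule and 5.5 is 150 − 90 = 60 days to 153 − 90 = 63 days.

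**Tiragolumab stopped first.** Let g be the days from the last tiragolumab dose to the last atezolizumab dose. Under 5.5, the period left after the last atezolizumab dose is max(0, 90 − g). With 28-day cycles and no delays:

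- one further atezolizumab cycle, g = 28: 90 − 28 = 62 days left
- two, g = 56: 34 days left
- three, g = 84: 6 days left
- four, g = 4 × 28 = 112: none left, the 90 days having ended 112 − 90 = 22 days before the last dose

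The Section 6.2 permission applies after an interruption of more than 12 weeks, which is more than 84 days. If the interruption is counted from the last tiragolumab dose, g exceeds 84 and fewer than 90 − 84 = 6 days can remain.

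**Study completion.** The end point in the last eligibility sentence is not defined for this purpose. Section 5.7 follows patients for 3 years from surgery, while the Protocol Summary gives a participant duration of 48 months. As an illustration, suppose that the first dose is given at 16 weeks (112 days) after surgery, that 13 cycles are given without delay, and that completion means the end of the 3-year follow-up. The last dose then falls on day 112 + 12 × 28 = 448, and the period ends 3 × 365 − 448 + 90 = 737 days after it. If completion means the end of treatment instead, the period is about 90 days. The three statements therefore cannot be treated as different wordings of one rule.

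**Pregnancy reporting.** Section 7.1.3 sets the reporting window at 90 days after tiragolumab or 5 months after atezolizumab, and Appendix C includes partners of male patients. The male period in 5.5 is shorter than this window by the same 60 to 63 days when both drugs end together. For atezolizumab alone, 5.5 states no post-treatment period against a 5-month window.

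**The case against.** The strongest reply is that the statements differ in length but do not exclude each other. Every man must agree to the eligibility item before treatment, and that item ties men to both drugs. Section 5.5 is silent about men after atezolizumab; it does not say that no period applies, nor that it overrides eligibility. Read together, every man in either arm has a post-treatment period, and a man who keeps to the longest one satisfies all of them. This stands, and it limits the point to an ambiguity. It does not remove it, because nothing in the protocol says that the longest period governs.

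The tiragolumab-only anchor may also be deliberate, since it appears in both sentences for men while the sentence for women names both drugs. That is possible. The protocol gives no such reason, though, and the eligibility item contradicts it. The documents do not show which section is the one in error.

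A reader might infer three stronger things that the documents do not support:

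- That men on atezolizumab alone have no post-treatment period anywhere in the protocol. Section 3.2.1 item 4 covers them.
- That the pregnancy reporting window is left undefined or cannot be matched to a contraception period. Section 7.1.3 defines it separately, it has the same two drug anchors as the first eligibility rule, and Appendix C extends reporting to partners of male patients.
- That 18 is the number of men affected, or its upper limit. It is the planned size of the arm for both sexes, and 5.5 applies only to men in certain partner situations. Simple randomization (Section 4.5) and replacement of Stage 1 patients (Section 5.3) can also move the arm size in either direction.

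**Conclusion.** The inconsistency is real. Sections 3.2.1 and 5.5 state different post-treatment periods for men, and the eligibility item itself contains two. Section 5.5 states no post-treatment period for men on atezolizumab alone, and none that is sure to outlast treatment for men who stop tiragolumab and continue atezolizumab. Eligibility still covers both groups. The number of men affected cannot be estimated, because the documents give no distribution by sex or partner status. The day counts rest on 5 months being 150 to 153 days and on undelayed 28-day cycles; the contradiction rests on the text alone. It warrants correction as a safety rule that gives one man more than one instruction, and it has no bearing on any endpoint, sample size or error rate.

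**What to change.** Reconcile Section 3.2.1 item 4 with Section 5.5 so that one period for men is stated for each treatment situation: both drugs, atezolizumab alone, and tiragolumab stopped early with atezolizumab continued. State whether the same period governs sperm donation and men with a pregnant partner. If study completion is kept as an end point, define it. Then check the result against the reporting window in Section 7.1.3. The clinical team must set the period; this review takes no view on its length.

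The cost is a wording amendment to the protocol, with the IRB review that any amendment needs. Whether the consent form needs the same change cannot be judged here, because its text was not available for review.

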5.6 Duration of Therapy

If at any time the constraints of this protocol are considered to be detrimental to the patient's health and/or the patient no longer wishes to continue protocol therapy, the protocol therapy should be discontinued and the reason(s) for discontinuation documented in the case report forms.

In the absence of treatment delays due to adverse events, treatment may continue for up to 13 cycles or until one of the following criteria applies:

- Documented and confirmed disease progression
- Death
- Adverse event(s) that, in the judgment of the investigator, may cause severe or permanent harm or which rule out continuation of study drug
- General or specific changes in the patient's condition render the patient unable to receive further treatment in the judgment of the investigator
- Suspected pregnancy
- Serious noncompliance with the study protocol
- Lost to follow-up
- Patient withdraws consent

- Investigator removes the patient from study
- The Siteman Cancer Center decides to close the study

Patients who prematurely discontinue treatment for any reason will still be followed as indicated in the study calendar with the exception of discontinuation due to disease recurrence; patients who stop treatment due to recurrence will be considered off study and will no longer be followed after the 90-day follow-up for adverse events is completed.

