5.7 Duration of Follow-up

Follow-up frequency is calculated from date of surgery. After surgery, patients will be followed every 12 weeks for 2 years and every 24 weeks for 1 additional year. Frequency and duration of follow-up after the end of treatment depends on when treatment is discontinued. Patients will be followed for 3 years from date of surgery regardless of when treatment is discontinued unless treatment is discontinued due to disease recurrence, in which case the patient will be considered off study after the 90-day follow-up for adverse events is completed. Patients removed from study for unacceptable adverse events will be followed until resolution or stabilization of the adverse event.

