14.0 STATISTICAL CONSIDERATIONS

14.1 Study Design

This is an open-label, multi-center, Simon two-stage phase II study consisting of random allocation of a portion of patients to a small reference arm to offer some protection against the uncertainties and potential biases of a one-armed study while retaining some of the statistical efficiency. The reference arm is not a control group in the traditional sense and there will not be a formal efficacy comparison between the treatment and reference groups (Herson and Carter, 1986; Rubinstein, et. al., 2009).

The purpose of this study is to evaluate the efficacy and safety of atezolizumab and tiragolumab in stage II melanoma patients who had undergone complete resection and been tested positive for circulating tumor DNA (ctDNA). In this study, the treatment arm (i.e., atezolizumab and tiragolumab) will not be compared with the reference arm (i.e., atezolizumab only); it will be analyzed against historical control as a one-armed study. The reference arm is intended to only act as a check on the similarity of the current patients to the historical control for a descriptive estimation of ctDNA clearance.

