14.3 Secondary Endpoints

- Confirmed ctDNA negative rate, defined as the proportion of ctDNA-positive patients having two consecutive negative ctDNA tests.
- Relapse free survival (RFS), defined as the duration of time from the date of positive ctDNA being confirmed to the date of earliest disease relapse or death, whichever occurs first. Patients who neither relapse nor die by the data cutoff date will be censored at the last follow up date.
- Distant metastasis free survival (DMFS), defined as the duration of time from the date of positive ctDNA being confirmed to the date of appearance of a distant metastasis or death, whichever occurs first. Patients who neither develop distant metastasis nor die by the data cutoff date will be censored at the last follow up date.
- Overall survival (OS), defined as the duration of time from the date of positive ctDNA being confirmed to death from any cause. Patients who are alive by the data cutoff date will be censored at the last follow up date.

- Safety and tolerability will be defined as the number of treatment (i.e., atezolizumab and tiragolumab) related grade 3 or greater adverse events (AEs). Adverse events will be assessed using CTCAE v5.0 criteria. Safety will be monitored from the time of initiation of study treatment to 30 days after discontinuation of therapy.

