14.7 Statistical Analyses

Descriptive statistics will be used to summarize the trial results. Statistics for continuous variables may include means, medians, ranges and appropriate measures of variability. Qualitative variables will be summarized by counts and percentages. The uncertainty of estimates will be assessed by confidence intervals (CIs). All analyses will be considered as exploratory, even if statistical tests will be used.

ctDNA clearance and confirmed negative rate, as well as safety data will be summarized by the number and proportions. RFS, DMFS, and OS will be presented via the Kaplan-Meier method. Median survival and corresponding two-sided 95% CIs will be computed. Survival rates with 95% CIs will be estimated. The group survival difference (i.e., treatment vs. reference) will be examined by the log-rank test. Further exploratory correlative analyses will be performed via Fisher exact test, t-test, or nonparametric Wilcoxon–Mann–Whitney test, if needed.

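### Patients who stop treatment for recurrence leave follow-up after 90 days, so overall survival is censored by prognosis and its Kaplan-Meier estimate is unreliable

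*Combined protocol and SAP*

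**What the plan says.** Two rules govern follow-up after treatment stops. The general rule in Section 5.7 is "Patients will be followed for 3 years from date of surgery regardless of when treatment is discontinued", and Section 5.6 agrees: "Patients who prematurely discontinue treatment for any reason will still be followed as indicated in the study calendar". Both sections then make recurrence the exception. Section 5.6 states that "patients who stop treatment due to recurrence will be considered off study and will no longer be followed" after the 90-day adverse-event period; Section 5.7 has "in which case the patient will be considered off study after the 90-day follow-up for adverse events is completed". A patient who relapses after completing treatment, or after stopping it for toxicity, falls under the general rule and stays in follow-up.

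Section 14.3 defines OS as time from confirmed positive ctDNA to death from any cause, with "Patients who are alive by the data cutoff date will be censored at the last follow up date". Section 14.7 presents OS by Kaplan-Meier and adds "The group survival difference (i.e., treatment vs. reference) will be examined by the log-rank test".

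Other provisions on deaths and contact do not fill the gap:

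- The follow-up column of the Schedule of Activities contains only CT.
- Sections 10.0 and 10.1 require a Death Form at the time of death but tell no one to look for deaths after a patient is off study.
- The post-study paragraph of Section 7.1.3 covers only serious events attributed to study drug.
- The contact attempts in Section 5.8 apply to missed study visits.

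**The concern.** Kaplan-Meier treats a censored patient as having the same later risk of death as those who remain. Here the reason for leaving is recurrence, which ordinarily raises that risk. The trial selects patients for early relapse: Section 1.2 reports that in a cited stage II/III study the majority of ctDNA-positive patients relapsed within 1 year of surgery, and treatment here runs for up to 13 four-week cycles. Those data do not give a relapse rate on study treatment, but the affected group may be large.

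At stake are the OS curve of each arm, its confidence interval (which does not show the bias), the log-rank contrast, and any analysis of ctDNA kinetics against OS. Section 2.0 gives comparison of OS between arms as a secondary aim. Distant metastasis-free survival is affected only when the recurrence that stops treatment is locoregional, because a distant recurrence is already an event.

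**Working it through.** **The plan's own figures.** The plan states no OS rate, event count or OS power. Its only design calculation is the Simon design in Section 14.5: continue with 3 or more clearances in 18, promising with 8 or more in 43. Exact binomial calculation gives one-sided type I error 0.048 and power 0.800, as stated. It depends only on ctDNA at C3D1, so the follow-up rule cannot change it.

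**Inputs for OS.** From the documents: exit about 3 months (90 days) after a relapse that stops treatment; about 12 months of treatment; all others followed to 3 years from surgery. Assumed, because the documents give none: 30% relapse in 12 months at a constant rate (varied 20-70%), median survival after relapse 24 months (varied 12-60), death without relapse 1% per year, and no later deaths captured. Time zero is the start of treatment.

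Monthly rates:

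- relapse: λ = −ln(1 − 0.30)/12 = 0.0297
- death after relapse: μ = ln 2/24 = 0.0289
- death without relapse: h = 0.01/12 = 0.00083

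**True OS.** Let A(t) = exp(−(λ + h)t) be the proportion alive and relapse-free. Then S(t) = A(t) + ∫₀ᵗ λA(r) exp(−μ(t − r)) dr.

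**OS under the plan.** Let B(t) be the same integral restricted to relapsed patients still followed: those who relapsed by month 12 and within 3 months before t, plus all who relapsed after month 12. Kaplan-Meier then estimates exp(−∫₀ᵗ [hA + μB]/[A + B]).

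| Month | True OS | OS under the plan | Difference (points) |
|---|---|---|---|
| 12 | 94.3% | 96.6% | +2.4 |
| 24 | 83.0% | 90.8% | +7.8 |
| 30 | 76.5% | 85.7% | +9.2 |

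Simulation gives the same 30-month result, and about half of the deaths by month 33 (48-49%) fall within follow-up. As a check, if relapse does not raise the death rate, the bias is zero.

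**Range.** Difference at 30 months, in points, by relapse proportion and median survival after relapse:

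| Relapse in 12 months | 12 mo | 24 mo | 36 mo | 60 mo |
|---|---|---|---|---|
| 20% | 9.4 | 6.7 | 5.0 | 3.3 |
| 30% | 12.7 | 9.2 | 6.9 | 4.5 |
| 50% | 16.3 | 12.3 | 9.4 | 6.2 |
| 60% | 16.7 | 12.9 | 9.9 | 6.6 |
| 70% | 16.2 | 12.9 | 10.0 | 6.7 |

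The top end fits Section 1.1 poorly. At the assumed 25% ctDNA-positive rate, a 12-month median with 50-70% relapse implies deaths in 13-16% of all stage II patients by 30 months (0.25 × 0.526 to 0.25 × 0.654). Section 1.1 implies five-year mortality of 6%, 13% and 18% for IIA, IIB and IIC.

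**If some later deaths are recorded.** Suppose a share of off-study deaths reaches the Death Form while off-study survivors stay censored at exit. Bias at 30 months, in points:

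| Share of later deaths captured | 0% | 25% | 50% | 75% | 100% |
|---|---|---|---|---|---|
| 30% relapse, 24-month median | +9.2 | +5.7 | +2.5 | −0.5 | −3.2 |
| 50% relapse, 24-month median | +12.3 | +5.6 | 0.0 | −4.8 | −8.8 |

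**Log-rank.** With identical arms of 43 and 18 under the plan's censoring, simulated two-sided 5% tests rejected in 4% to 5% of 10,000 trials. For 30% against 50% relapse, power was about 13%, compared with 18-19% under full follow-up. The contrast also shrinks. With 20% and 50% relapse and a 24-month median, true 30-month OS is 82.9% and 65.5% (17.4 points apart), whereas the plan would show 89.7% and 77.8% (11.9 apart).

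**The case against.** A reader might infer that OS will certainly be overstated. The documents do not support that. The Death Form is due at time of death, and neither Section 10.0 nor 10.1 limits it to patients on study. Sites may hear of deaths, and counting them while survivors stay censored can reverse the sign, as shown above. This objection stands: the direction is conditional. It does not rescue the estimate, which would then depend on which deaths sites happened to learn of.

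A reader might also infer that the log-rank test would give too many false positives. The runs above do not show this; the cost is lost power and a distorted contrast.

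The size can be challenged. Section 14.7 names no landmark, and the Protocol Summary puts the primary analysis after all patients complete adjuvant therapy, when late entrants have short follow-up; earlier landmarks give smaller bias. The thirteenth dose falls at week 48, so only relapses in about 11 months can stop treatment, which lowers the 30-month figure from 9.2 to 8.5 points. Both objections stand and are reflected in the figures given.

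Finally, OS is secondary. Section 14.7 says "All analyses will be considered as exploratory, even if statistical tests will be used", and Section 14.1 says "there will not be a formal efficacy comparison between the treatment and reference groups". The central bias is also below single-arm sampling error: 1.96 × √(0.76 × 0.24/n) is 12.8 points for n = 43 and 19.7 for n = 18. This limits the weight of the point, but an exploratory label does not correct a systematic error that the confidence interval leaves out.

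**Conclusion.** Wrong as written. This is an explicit rule that yields informatively censored OS, not a missing detail. OS is biased upward if few later deaths are recorded; the bias shrinks, and may reverse, if most are learned of passively while survivors remain censored at the off-study date. In the illustrative case with none recorded, the excess is about 2 points at 12 months, 8 at 24 and 9 at 30 (8.5 with an 11-month window). It is roughly 3 to 17 points at 30 months over the assumed ranges, with the top end least plausible. These sizes rest on assumed relapse and post-relapse survival rates.

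It would go too far to extend this to the trial's main conclusion. C3D1 clearance, the Simon rule and the sample size are unaffected. For distant metastasis-free survival the problem is confined to locoregional recurrences that stop treatment, and no direction is claimed.

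**What to change.** In Sections 5.6 and 5.7, replace the off-study exception with continued vital-status follow-up for patients who stop treatment for recurrence. Use chart review or telephone at each data cutoff and at 3 years from surgery, recorded on the existing Follow Up and Death forms. The date of first distant metastasis can be taken from the same chart review, with a note that detection is less regular than by scheduled CT.

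In Section 14.3, state that OS is not censored at recurrence or at the end of treatment, that patients not known to have died are censored at the date last known alive, and that vital status is sought for all patients at a common cutoff. The common cutoff is essential: collecting deaths without updating survivors would replace an upward bias with a possible downward one.

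The cost is an amendment, consent wording and periodic checks on about 12 to 43 patients (0.20 × 61 to 0.70 × 61 under the assumed relapse range). No visits or scans are added. Patients already off study may need re-contact or IRB agreement for record review. A caveat or sensitivity analysis alone would be cheaper but would not recover the missing deaths.
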